3.3.3 Adverse events of special interest

The protocol specifies Adverse Events of Special Interest (AESIs) as those which merit special attention in this trial, and for which derivation details (for those derived from the eCRF), or a statement when the derivation needs to be referenced externally to the SAP (for those derived from MedDRA dictionary terms), are given in [Appendix 8.1](#).

3.3.4 Laboratory variables

Clinical chemistry, haematology and urinalysis will be performed by a central laboratory according to the schedule and the variable specifications described in the CSP. Urine samples will be analysed locally and sent for analysis at the central laboratory only if a positive dipstick result for any parameter is observed.

Changes from baseline in continuous laboratory variables will be calculated at relevant visits as specified in [Section 3.1.1](#) and [Section 3.1.2](#).

In all analyses of continuous laboratory variables, any value recorded only as below Lower Limit of Quantification (LLOQ) will be set to LLOQ and included in the analysis. Any value recorded only as above Upper Limit of Quantification (ULOQ) will be set to ULOQ and included in the analysis.

Absolute values will be compared to the relevant normal reference range, as provided by the central laboratory, and classified as low (below range), normal (within range or on the limits)

or high (above range). All values falling outside the normal reference ranges will be flagged. These classifications will also be used for shift tables.

For the purposes of shift tables, baseline will be defined as specified in [Section 3.1.1](#). Minimum, maximum and last values calculated across all visits in the relevant study period will use all available values, including those from unscheduled and repeat visits, and irrespective of whether the values have been selected for use in summaries using visit windows (see [Section 3.1.5](#)).

Liver function tests will also be evaluated as multiples of the upper limit of the normal reference range (ULN). Subjects who meet any of the following criteria at any time during the study will be flagged:

- AST $\geq 3 \times$ ULN
- ALT $\geq 3 \times$ ULN
- TBL $\geq 2 \times$ ULN

Other multiples of ULN will also be used in the display of liver function tests.

3.3.5 Vital signs

Changes from baseline in vital signs (pulse rate, systolic blood pressure (BP), diastolic BP, respiratory rate, body temperature, body weight and body mass index (BMI)) will be calculated at relevant visits as specified in [Section 3.1.1](#) and [Section 3.1.2](#).

BMI is calculated as:

$$BMI = Weight (kg) / [Height (m)]^2.$$

Absolute values and changes from baseline (where applicable) will be compared to the relevant reference range tabulated below, and classified as low (below range), normal (within range or on the limits) or high (above range). All values falling outside the reference ranges will be flagged.

Table 6 Vital signs reference ranges

Parameter	Standard Units	Lower Limit	Upper Limit	Change from Baseline Criteria
Diastolic BP (sitting)	mmHg	60	100	± 15
Systolic BP (sitting)	mmHg	90	160	± 30
Pulse rate (sitting)	beats/min	50	100	± 20

Parameter	Standard Units	Lower Limit	Upper Limit	Change from Baseline Criteria
Respiratory rate	breaths/min	8	20	
Body temperature	Celsius	36.0	37.5	
Weight	kg	40	150	

3.3.6 12-lead digital ECG

The outcome of the overall evaluation (normal, abnormal or borderline) will be taken directly from the eCRF, as will the assessment of clinical significance.

Changes from baseline in continuous 12-lead ECG variables (data provided external to the eCRF) will be calculated at relevant visits as specified in [Section 3.1.1](#) and [Section 3.1.2](#).

3.3.7 Physical examination

Only physical examination results judged as a new clinically meaningful finding or a clinically meaningful aggravation of an existing finding by the investigator will be captured, and these will be reported as AEs.

3.3.8 Medical history

If a partial diagnosis date is available only, the following rules will be used to impute a complete date (e.g. for derivation of time since diagnosis):

If both the month and the year are available, the first of the recorded month will be imputed, unless the date of birth is within the same month and year (where date of birth is available, which will not be the case in all countries). In this case, the date of birth will be imputed instead.

If only the year is available, 1st January will be imputed, unless the date of birth is within that same year (where date of birth is available). In this case, the date of birth will be imputed instead.

3.4 Derivation of pharmacokinetic and immunogenicity variables

Serum samples for determination of tezepelumab concentrations and the presence of anti-drug antibodies (ADA) and neutralising antibodies (nAb) will be collected at baseline prior to first IP administration, at multiple time points before IP administration during the treatment period, and at selected timepoints in the follow-up period, according to the CSP schedule of assessments.

Samples will be used to determine tezepelumab concentrations, and to measure the presence of ADA and nAb, according to validated assays performed by a designated third party vendor. Details of the bioanalytical methods used will be described in a separate bioanalytical report.

For immunogenicity, tiered analysis will be performed to include screening, confirmatory, and titre of ADA assay components as well as nAb assay. Samples that are confirmed positive for ADAs will be further analysed for the presence of nAb.

The third party vendor analysing the PK samples will be unblinded to the randomised treatment assignments of all subjects; no one from the study team will have access to the PK or ADA data until after the study has been unblinded. The assay for determination of tezepelumab concentrations will only be performed using samples for subjects randomised to tezepelumab. Subjects who are randomised to placebo will not have their PK samples analysed by the vendor laboratory. The ADA samples from all subjects, regardless of treatment assignment, will be analysed.

Due to the limited sampling schedule, only serum concentration data will be available (for the tezepelumab group only); no other PK parameters will be derived for any analysis within the scope of this SAP.

4. ANALYSIS METHODS

4.1 General principles

4.1.1 Statistical hypotheses for confirmatory endpoints

The following two-sided hypotheses will be evaluated in this trial. The nominal significance levels and methodology for accounting for multiplicity in testing these hypotheses is described in [Section 4.1.2](#).

Primary endpoint – all subjects

H01: AAER ratio over 52 weeks (tezepelumab/placebo) = 1

versus

H11: AAER ratio over 52 weeks (tezepelumab/placebo) \neq 1

The direction of superiority of tezepelumab is indicated by a rate ratio less than 1.

AAER – subjects with baseline eosinophils < 300/ μ L

H02: AAER ratio over 52 weeks (tezepelumab/placebo) = 1

versus

H12: AAER ratio over 52 weeks (tezepelumab/placebo) \neq 1

The direction of superiority of tezepelumab is indicated by a rate ratio less than 1.

Key secondary endpoints – all subjects

H03: Difference in mean change from baseline in pre-BD FEV₁ at 52 weeks
(tezepelumab minus placebo) = 0

versus

H13: Difference in mean change from baseline in pre-BD FEV₁ at 52 weeks
(tezepelumab minus placebo) ≠ 0

The direction of superiority of tezepelumab is indicated by a difference in means greater than 0.

H04a: Difference in mean change from baseline in AQLQ(S)+12 total score at 52 weeks
(tezepelumab minus placebo) = 0

versus

H14a: Difference in mean change from baseline in AQLQ(S)+12 total score at 52 weeks
(tezepelumab minus placebo) ≠ 0

The direction of superiority of tezepelumab is indicated by a difference in means greater than 0.

H04b: Difference in mean change from baseline in ACQ-6 score at 52 weeks (tezepelumab
minus placebo) = 0

versus

H14b: Difference in mean change from baseline in ACQ-6 score at 52 weeks (tezepelumab
minus placebo) ≠ 0

The direction of superiority of tezepelumab is indicated by a difference in means less than 0.

H05: Difference in mean change from baseline in weekly mean Asthma Symptom Diary score
at 52 weeks (tezepelumab minus placebo) = 0

versus

H15: Difference in mean change from baseline in weekly mean Asthma Symptom Diary score
at 52 weeks (tezepelumab minus placebo) ≠ 0

The direction of superiority of tezepelumab is indicated by a difference in means less than 0.

4.1.2 Testing strategy for confirmatory endpoints

The overall Type 1 error rate will be strongly controlled at the 0.05 level across the primary and key secondary endpoints. The primary endpoint (in all subjects) will be tested at the 0.01 level to further ensure statistically persuasive evidence. If the primary analysis of AAER in all subjects observes $p \leq 0.01$, the trial will be declared successful. In order to assess the primary objective of effect across the all-comer population, the subgroup of subjects with baseline eosinophils $< 300/\mu\text{L}$ has been added into the multiple testing procedure following direction from the FDA.

The following hierarchical testing strategy will be applied, ordered by clinical relevance:

Level 1

The null hypothesis H01 will be tested at a 2-sided 1% significance level regarding the primary endpoint (AAER) in all subjects.

Level 2

If H01 is rejected at the 2-sided 1% significance level, then the null hypothesis H02 will be tested at a 2-sided 5% significance level regarding the AAER in subjects with baseline eosinophils $< 300/\mu\text{L}$.

Level 3

If H02 is rejected at the 2-sided 5% significance level, then the null hypothesis H03 will be tested at a 2-sided 5% significance level regarding change from baseline in pre-BD FEV₁.

Level 4

If H03 is rejected at the 2-sided 5% significance level, then the null hypotheses H04a and H04b will be simultaneously tested at an overall 2-sided 5% significance level regarding:

- change from baseline in AQLQ(S)+12 total score
- change from baseline in ACQ-6 score

using a truncated Hochberg approach. In general, under this approach, the higher of the two ordered p-values within Level 4 will be evaluated at a $\gamma\alpha + (1-\gamma)\alpha/2$ significance level (2-sided), and the lower of the 2 ordered p-values within Level 4 will be evaluated at a $\gamma\alpha/2 + (1-\gamma)\alpha/2$ significance level (2-sided), where $\alpha = 0.05$, and where γ is the truncation parameter ($0 \leq \gamma \leq 1$).

It is noted an intermediate choice $0 < \gamma < 1$ of the truncation parameter represents a choice between these extremes of regular Hochberg (corresponding to $\gamma = 1$) and Bonferroni approaches ($\gamma = 0$), balancing considerations of how stringent hypothesis testing should be in Level 4 in order to claim significance, versus the ability to subsequently claim significance from formal hypothesis testing in Level 5. In this trial γ will be set to 0.5.

Using this choice of truncation parameter, the higher of the two Level 4 p-values will be evaluated at a 3.75% significance level (2-sided). If it is significant at the 3.75% level, then both hypotheses H04a and H04b will be rejected, and testing will proceed to Level 5. If it is not significant at the 3.75% level, then the lower of the 2 Level 4 p-values will be evaluated at a 2.5% significance level (2-sided). If it is significant, then the relevant null hypothesis (either H04a or H04b) will be rejected, and testing will proceed to Level 5. If it is (also) not significant, then formal testing will stop at Level 4. The significance levels for subsequent evaluation in Level 5 for each of these scenarios are given below.

Level 5

[figure not shown]
The null hypothesis H05 will be tested at the significance level retained from Level 4, which depends on the outcomes in Level 4 as follows:

- Case 1: If both comparisons in Level 4 exhibit statistical significance, then H05 will be tested at a 2-sided 5% significance level with regard to change from baseline in weekly mean ASD score.
- Case 2: If only one of the comparisons in Level 4 exhibits statistical significance, then H05 will be tested at the 2-sided significance level $\alpha - [\gamma\alpha + (1-\gamma)\alpha/2]$ retained from Level 4, where $\alpha = 0.05$.

Using the proposed choice of $\gamma = 0.5$, if both H04a and H04b were rejected in Level 4, then H05 in Level 5 will be tested at a 2-sided 5% significance level (Case 1). If only one of H04a and H04b was rejected in Level 4, then H05 in Level 5 will be tested at a 2-sided 1.25% significance level (Case 2).

The multiple testing procedure is summarised graphically in the following figure:

Figure 1 Multiple testing procedure

4.2 Analysis methods

4.2.1 Subject disposition, demography and baseline characteristics

Subject disposition will be summarised using the all subjects analysis set. The number of enrolled subjects will be summarised. The number and percentage of subjects within each treatment group will be presented by the following categories; randomised, not randomised

(and reason), received IP, did not receive IP (and reason), completed treatment, discontinued treatment (and reason), completed study (subjects who completed IP and study, and subjects who discontinued IP but completed study assessments), and discontinued study (including reason). Subject recruitment by country and centre will also be summarised.

Disposition summaries will also include the number and percentage of randomised subjects who subsequently participated in the planned extension study.

Disposition will also be provided for the number and percentage of randomised subjects who consented separately to participate in the optional sub-studies (DNA sampling, flow cytometry, home-based FENO).

The number and percentage of subjects, who discontinued IP, but remained in the study will be presented by treatment group and option of follow up ([Section 1.2](#)).

Disposition summaries will also be produced for the age subgroups at study entry: adults (≥ 65), adults (≥ 18 to < 65) and adolescents (≥ 12 to < 18).

Kaplan-Meier plots will be produced summarising separately the time (in days) to last dose of IP and premature withdrawal from the study. Subjects without the premature event will be censored as described in [Section 3.1.8](#).

Demographic data, such as age, gender, and race, will be summarised by treatment group for the FAS. Stratification factors recorded at randomisation by the IXRS will be summarised by treatment for the FAS. All subgroups as defined in [Section 3.1.7](#) will be summarised by treatment group for the FAS.

Various baseline characteristics will also be summarised by treatment for the FAS. These include medical, surgical and respiratory disease histories, weight, height and BMI, smoking status, history of allergy, FEV₁ (pre and post-BD) and FEV₁ reversibility, FEV₁ %predicted, FEF_{25-75%} (pre and post-BD), asthma duration, age at onset of asthma, asthma medications, the number of asthma exacerbations in the previous 12 months, number of asthma exacerbations requiring hospitalisations in the previous 12 months, AQLQ(S) +12 and ACQ-6.

Baseline biomarker variables (FENO, eosinophils and IgE) will also be summarised by treatment for the FAS.

Demographic data, various baseline characteristics and baseline biomarker variables will also be summarised by treatment and the following categorical variables for the FAS:

- Baseline eosinophils group: $< 300/\mu\text{L}$, $\geq 300/\mu\text{L}$
- Age subgroups at study entry: adults (≥ 65), adults (≥ 18 to < 65) and adolescents (≥ 12 to < 18).

Medical and surgical histories will be summarised by MedDRA Preferred Term (PT) within the System Organ Class (SOC) level of MedDRA.

Important PDs will be summarised by treatment for the FAS.

The number and percentage of subjects in each of the analysis sets defined in [Section 2.1](#) will be summarised.

4.2.2 Prior and concomitant medication

The number and percentage of subjects receiving each medication (by ATC classification system codes and generic name) will be presented by treatment for the FAS. Separate tables will be presented for all medications received during each of the following periods as defined in [Section 3.1.6](#): Prior, Concomitant (on-treatment), Concomitant (post-treatment).

Tables for maintenance medications (started prior to and ongoing after the first day of IP) will be produced displaying the baseline total daily dose categories (low/medium/high) of ICS medications. The number of subjects using other maintenance asthma medications at baseline will also be summarised. In addition, the total number of days of systemic corticosteroid treatment associated with asthma exacerbations per patient from the first day of IP up to Week 52 will also be summarised.

The number of subjects using other maintenance asthma medications at baseline will also be summarised for the age subgroups at study entry: adults (≥ 65), adults (≥ 18 to < 65) and adolescents (≥ 12 to < 18).

Summary statistics will be produced of total daily OCS dose converted to a prednisone equivalent (for subjects taking OCS at baseline). Conversion factors to be applied for this purpose are given in [Appendix 8.2](#).

A separate table will be presented for subjects who took disallowed concomitant medications.

Disallowed medications will include medications defined as prohibited according to Section 6.5 of the CSP. Disallowed medications include prohibited and restricted drugs; restricted drugs are considered a disallowed medication depending on timing of use, or if there are changes in dose and regimen during the study as defined in the CSP. They will be defined following a physician review (prior to primary database lock) of the unique combinations of ATC code classifications and generic terms captured.

Medications will be classified using the latest version of the WHO Drug Dictionary.

Percentages will be calculated relative to the number of subjects in the FAS.

Data from subjects who discontinued IP, regardless of level of follow up chosen will, where possible and relevant, be included in the appropriate medication summaries.

Potential prior biologics use will be summarised separately, similarly to above.

4.2.3 Exposure and compliance

Exposure and treatment compliance derivation details are defined in [Section 3.3.1](#).

Extent of exposure to IP, compliance, and total number of dosing occasions will be summarised by treatment group, for the safety analysis set. These data will also be summarised for the age subgroups at study entry: adults (≥ 65), adults (≥ 18 to < 65) and adolescents (≥ 12 to < 18).

The date and time of IP administrations, and all missed doses will be listed using the safety analysis set.

Compliance with the regularly scheduled ICS/LABA asthma inhaler as recorded in the daily diary will be summarised by each weekly period and treatment group, together with the compliance of the use of the daily diary. These data will also be summarised for the age subgroups at study entry: adults (≥ 65), adults (≥ 18 to < 65) and adolescents (≥ 12 to < 18).

4.2.4 Primary endpoint

4.2.4.1 Primary analysis

The primary analysis of the primary efficacy endpoint (AAER over 52 weeks) will quantify the effect of the initially randomised treatment, regardless of the treatments that subjects actually received, or whether the subjects received other controller therapy/rescue medications post IP discontinuation.

This analysis uses a treatment policy strategy and will therefore include all available data after treatment discontinuation until the end of the planned treatment period.

Subjects will be encouraged to continue to undergo applicable study related visits/procedures for the full 52-week period even after premature discontinuation of IP. Consequently, subjects lost to follow-up, subjects who die and subjects who withdraw their consent should be the only source of missing information for the primary analysis.

Missing data from early study withdrawal will be modelled based on what was observed during the study using direct likelihood approaches, which is a valid approach under the assumption that data are missing at random (MAR).

AAER in the tezepelumab group will be compared to that seen in the placebo group using a negative binomial model. This model will be used to perform the statistical test of the null hypothesis specified in [Section 4.1.1](#) and to estimate the treatment effect and both its 99% and 95% confidence intervals.

The response variable in the model will be the number of asthma exacerbations experienced by a subject over the 52-week planned treatment period (or shorter duration if not followed up

for the full 52 weeks). Treatment, region, age (adolescents or adults) and history of exacerbations (≤ 2 or > 2 in previous 12 months) will be included as factors in this model. Any subject who is incorrectly randomised with a history of fewer than 2 exacerbations will be included in the primary analysis. The logarithm of the time at risk (in years) for exacerbation will be used as an offset variable in the model, to adjust for subjects having different follow-up times during which the events occur. Time during an exacerbation and the 7 days following an exacerbation in which a new exacerbation cannot occur, will not be included in the calculation of time at risk for exacerbation. For all further primary endpoint derivation details, see [Section 3.2.1](#).

Descriptive summaries of the asthma exacerbations will also be presented. Unadjusted exacerbation rates will be summarised using an approach weighted by subject's time at risk (i.e. the total number of exacerbations for each treatment divided by the total time at risk for that treatment).

Adjusted (model-based) exacerbation rates will be presented using the marginal rates approach described in [Bartlett \(2018\)](#).

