9.2 Sample size determination

Approximately 1060 subjects will be randomly assigned to study treatment using 1:1 allocation between the two treatments. Since the primary analysis of the primary endpoint will include all available data, including after treatment discontinuation, no need is envisaged to adjust the number of subjects planned to be randomized in order to obtain a number of evaluable subjects.

With 530 subjects per treatment group it is estimated that, using the multiple testing procedure described in Section 9.4 with an overall Type 1 error control at $\alpha=0.05$ and a Type 1 error control for the primary endpoint at $\alpha=0.01$, the power for the primary and the key secondary endpoints will be at least 90%. The Type 1 error control at $\alpha=0.01$ for the primary endpoint is chosen to further ensure statistically persuasive evidence.

For the primary endpoint (in all subjects), assuming a placebo rate of 0.9, a shape parameter of 2.4 (over-dispersion) and a dropout rate of 10% (uniform over the study), there will be >99% power to detect a rate reduction of 50% at a 2-sided significance level of 1%. The methodology used is described in [Keene et al, 2007](#) and [Zhu and Lakkis 2014](#). The minimum detectable rate reduction with the above assumptions is 27%.

For AAER in subjects with baseline eosinophils < 300/ μ L, assuming a placebo rate of 0.6 and assuming that half of subjects will be in this subgroup (i.e. 265 subjects per treatment group), there will be 94% power to detect a rate reduction of 50% at a 2-sided significance of 5%, with the same shape parameter and dropout assumptions as above.

For each of the key secondary endpoints, change from baseline in pre-bronchodilator FEV1, change from baseline in AQLQ(S)+12 total score, change from baseline in ACQ-6, and change from baseline in weekly mean Asthma Symptom Diary score, the nominal power is 95% or higher, assuming standard deviations of 400 mL and 1.3, 1.3, and 1.3 units respectively, and true differences of 100 mL and 0.3, 0.3, and 0.3 units respectively. The minimum detectable differences being significant, under the above assumptions are 50 mL for FEV1, 0.16 for AQLQ(S)+12 total score, and -0.16 for each of Asthma Symptom Diary score and ACQ-6 score.

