1.3 Number of subjects

Approximately 1060 subjects will be randomly assigned to study treatment using 1:1 allocation between the two treatments. Since the primary analysis of the primary endpoint will include all available data, including after treatment discontinuation, no need is envisaged to adjust the number of subjects planned to be randomised in order to obtain a number of evaluable subjects.

With 530 subjects per treatment group it is estimated that, using the multiple testing procedure described in [Section 4.1.2](#) with an overall Type 1 error control at $\alpha=0.05$ and a Type 1 error control for the primary endpoint at $\alpha=0.01$, the power for the primary and the key secondary endpoints will be at least 90%. The Type 1 error control at $\alpha=0.01$ for the primary endpoint is chosen to further ensure statistically persuasive evidence.

For the primary endpoint, assuming a placebo rate of 0.9 per year, a shape parameter of 2.4 (overdispersion), and a dropout rate of 10% (assumed uniform over the study), there will be at least 99% power to detect a rate reduction of 50% at a 2-sided significance level of 1%. The methodology used is as described in [Keene et al., 2007](#), and developed further by [Zhu and Lakkis, 2014](#). The minimum rate reduction that would yield statistical significance with the above assumptions is 27%.

For AAER in subjects with baseline eosinophils $< 300/\mu\text{L}$, assuming a placebo rate of 0.6 and assuming that half of subjects will be in this subgroup (i.e. 265 subjects per treatment group), there will be 94% power to detect a rate reduction of 50% at a 2-sided significance level of 5%, with the same shape parameter and dropout assumptions as above.

For each of the following four key secondary endpoints, change from baseline in pre-BD FEV₁, change from baseline in AQLQ(S)+12 total score, change from baseline in ACQ-6, and change from baseline in weekly mean Asthma Symptom Diary score, the nominal power is 95% or higher (using a nominal 2-sided significance level of 5%), assuming standard deviations of 400 mL and 1.3, 1.3, and 1.3 units respectively, and true differences of 100 mL and 0.3, 0.3, and 0.3 units respectively. The minimum detectable differences, under the above assumptions, are 50 mL for FEV₁, 0.16 for AQLQ(S)+12 total score, and -0.16 for each of Asthma Symptom Diary score and ACQ-6 score.

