A blinded review of subjects who discontinued IP for reasons of “Subject lost to follow-up”, “Subject decision” or “Other” will be performed prior to unblinding at the primary database lock. A listing of these subjects and the assumptions made under DRMI will be documented. If any recorded comments (on either of the “Discontinuation of Investigational Product” or “Disposition” eCRF pages) indicate clearly that the reason for study withdrawal was not related to treatment, then the “Placebo” default for DRMI in the above table may be changed for that subject.

The methodology used for sensitivity analysis is described in more detail in [Keene et al., 2014](#). The steps for carrying out multiple imputation are outlined below.

Step 1: Fitting a negative binomial model to the observed data

A negative binomial regression model will be fitted to the observed exacerbation data with treatment group, region, age and history of exacerbations included as covariates. The logarithm of the time at risk (in years) for exacerbation will be used as an offset variable in the model.

Step 2: Drawing samples from the posterior distribution

The negative binomial distribution is conventionally defined as the probability distribution of the number of successes Y before k failures are seen in a series of independent Bernoulli trials with probability p of success and $(1-p)$ of failure.

The posterior distribution for parameter k and coefficients β will be created as a product of non-informative prior and the likelihood from the model in Step 1. A uniform prior distribution will be assumed for the regression coefficients. A Gamma (10^{-4} , 10^{-4}) will be assumed for $1/k$.

With the use of Markov Chain Monte Carlo (MCMC) method, 100 samples of k and β will be drawn from their posterior distribution. Convergence of the MCMC algorithm will be assessed.

A random seed of 991511 will be used. The first 2000 iterations will be discarded to allow for convergence to a stationary distribution and to remove the effect of the starting values (“burn-in”). A gap of 100 iterations will be used between imputations to ensure independence between imputations (“thinning”).

Step 3: Imputing missing data

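### The primary exacerbation-rate model could also adjust for baseline eosinophil group, which the plan's own placebo rates make prognostic; the gain is small and the current test is valid

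*SAP*

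**What the plan says.** The factors of the primary model are "Treatment, region, age (adolescents or adults) and history of exacerbations" (SAP 4.2.4.1), with log time at risk as offset. Protocol 9.4.3.1 gives the same model. The negative binomial model behind the missing-data analyses is fitted "with treatment group, region, age and history of exacerbations included as covariates" (SAP 4.2.4.2, Step 1), and the model for the completed counts in Step 4(iv) has the same terms.

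Randomisation is stratified by region and age group only (Protocol 4.1 and 6.3; SAP 1.2). Recruitment is steered towards similar numbers below and at or above 300 eosinophils/µL. That fixes the overall mix but does not balance the two arms.

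The sample size for all subjects is derived "assuming a placebo rate of 0.9 per year" (SAP 1.3). For the low-eosinophil group it is derived "assuming a placebo rate of 0.6 and assuming that half of subjects will be in this subgroup" (Protocol 9.2).

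Eosinophil group and its interaction with treatment appear only in the separate subgroup model of SAP 4.2.4.5, which supplies the Level 2 test. No eosinophil-adjusted overall rate ratio is planned.

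**The concern.** A baseline variable that predicts the outcome, is measured in all subjects before dosing and is not used in stratification is a natural covariate. On the plan's own assumptions, the placebo rate at or above 300/µL is twice the rate below it. Leaving the variable out puts known between-subject variation into the dispersion parameter and slightly widens the confidence intervals. It also leaves the estimate uncorrected if the arms happen to differ in eosinophils. In that event readers would ask for an adjusted estimate, and one specified after unblinding carries less weight than one specified now.

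**Working it through.** **Inputs** (SAP 1.3, Protocol 9.2): 530 subjects per arm; placebo rate 0.9; dispersion k = 2.4; 10% uniform dropout, so mean follow-up t = 0.9 × 1 + 0.1 × 0.5 = 0.95 year; rate ratio 0.5; two-sided 1%. Low-eosinophil group: 265 per arm, placebo rate 0.6, two-sided 5%.

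**1. The plan's figures reproduce.** Var(log RR) = [1/(μ₀t) + 1/(μ₁t) + 2k]/n.
- All subjects: (1.170 + 2.339 + 4.8)/530 = 0.01568, SE 0.1252. Power = Φ(0.693/0.1252 − 2.576) = 99.8% (stated: at least 99%).
- Below 300/µL: (1.754 + 3.509 + 4.8)/265 = 0.03797, SE 0.1949. Power = Φ(0.693/0.1949 − 1.960) = 94.5% (stated: 94%).
- Smallest significant reduction in all subjects: 26.5%, or 26.7% with t = 0.90. The SAP states: "The minimum rate reduction that would yield statistical significance with the above assumptions is 27" (per cent).

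**2. Implied rate at or above 300/µL.** (0.9 − 0.5 × 0.6)/0.5 = 1.2, twice 0.6. If the low group were 40% or 60% of subjects, the implied rate would be 1.10 or 1.35, a ratio of 1.8 to 2.25.

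**3. Dispersion left after adjustment.** If 2.4 is the overall dispersion, the total variance of the subject rates is 2.4 × 0.9² = 1.944. The between-group part is 0.3² = 0.09. The mean squared group rate is (0.36 + 1.44)/2 = 0.9. The within-group dispersion is therefore k′ = (1.944 − 0.09)/0.9 = 2.06.

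**4. Gain by formula, common rate ratio 0.5.**
- Low group: (1.754 + 3.509 + 4.12)/265 = 0.03541.
- High group: (0.877 + 1.754 + 4.12)/265 = 0.02548.
- Combined: 1/(1/0.03541 + 1/0.02548) = 0.01482, SE 0.1217.

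| | Without eosinophils | With eosinophils |
|---|---|---|
| SE(log RR) | 0.1252 | 0.1217 (−2.8%; variance −5.5%) |
| 99% CI at RR 0.50 | 0.362 to 0.690 | 0.365 to 0.684 |
| Power at 1% | 99.8% | 99.9% |

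If 2.4 is instead the within-group dispersion, the SE goes from 0.131 to 0.127 and power from 99.7% to 99.8%.

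**5. Gain by simulation.** Four scenarios (rate ratio 0.5 or 1; within-group dispersion 2.06 or 2.4), 1,500 trials each. The model SE fell by 1.4 to 1.9% and the empirical SD of log RR by 2.0 to 4.4%. The mean log RR was essentially the same with and without the factor. Type I error at the 1% level was 1.2 to 1.4% without it and 0.9 to 1.1% with it. The simulation standard error is √(0.01 × 0.99/1500) = 0.26 points, so all of these are compatible with 1%.

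**6. Chance imbalance.** The SD of the between-arm difference in the share at or above 300/µL is √(2 × 0.25/530) = 3.1 points. A 1.96-SD difference is 6.0 points. The unadjusted rate ratio then moves by a factor of (0.6 × 0.4699 + 1.2 × 0.5301)/(0.6 × 0.5301 + 1.2 × 0.4699) = 0.918/0.882 = 1.04. One SD moves it by about 2%.

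**7. If the rate ratio is not common.** The values below are illustrative assumptions, fitted to large simulated data sets with placebo rates 0.6 and 1.2.
- Rate ratios 0.7 (low) and 0.3 (high): the overall ratio is (0.42 + 0.36)/1.8 = 0.433. One data set gave 0.427 unadjusted and 0.444 adjusted; another gave 0.436 and 0.453. The shift is about 4% and the SE gain about 0.2%.
- Rate ratios 0.6 and 0.4: the overall ratio is (0.36 + 0.48)/1.8 = 0.467. The fits gave 0.465 and 0.477, a shift of about 2.5%, with an SE gain of about 1%.

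**The case against.** The strongest reply is that nothing turns on this. Power is above 99% with or without the factor, the interval barely changes, and the model already holds both stratification factors and exacerbation history. If history is correlated with eosinophils, the gain is smaller than calculated here. The rate of 1.2 is inferred, and 0.6 may be a cautious planning value. An imbalance would also be visible, because SAP 4.2.1 tabulates eosinophils by treatment. All of this stands, and it is why the point is minor.

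It also stands that adjustment is not free of consequences. The overall rate ratio keeps its meaning only if the effect is the same in both eosinophil groups, which the plan does not presume: it tests the low group separately. Step 7 shows that otherwise the adjusted ratio can shift by as much as the imbalance it is meant to correct.

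Three stronger readings are tempting but unsupported:
- A reader might infer that missing counts are imputed at one rate regardless of eosinophils. SAP 4.2.4.2 conditions on each subject's observed events (k* = k + Y₁) and on region, age and history, so prognosis is partly used.
- A reader might see a defect in the Level 1 and Level 2 models adjusting differently. The Level 2 model needs the eosinophil term to estimate an effect within that group; Level 1 asks an overall question.
- A reader might count imprecision and chance imbalance as two harms. Averaged over randomisations, imbalance is part of the same lost precision.

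**Conclusion.** The point holds as a low-severity improvement. The primary model omits a covariate that the plan's own figures make prognostic. Including it would reduce SE(log RR) by about 1.5 to 4% and protect the estimate against a shift of about 4% in an unlucky (2-SD) allocation. The documents do not support a claim that the primary test is biased, invalid or underpowered.

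The size rests on four assumptions: the 0.9 and 0.6 rates describe the same population; about half of subjects fall in each group; the rate ratio is common to both; and region, age and exacerbation history, left out of the calculation, do not already carry much of the eosinophil information. If the third fails, most of the gain goes. Whether the Level 2 test needs its own missing-data sensitivity analyses is a separate question and adds no weight here.

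**What to change.** Before unblinding, choose one of two options.

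1. Add baseline eosinophil group (<300, ≥300/µL) as a factor in the model of SAP 4.2.4.1 and Protocol 9.4.3.1, and in Steps 1 and 4(iv) of SAP 4.2.4.2. The baseline rule in SAP 3.1.1 already takes the last non-missing value up to randomisation, so Visit 1 serves when Visit 3 is missing. State that in the eosinophil subgroup models of SAP 4.2.4.5 the subgroup's own categories replace this factor, as is already done for age.
2. Leave the primary model unchanged and pre-specify the eosinophil-adjusted overall rate ratio as a sensitivity analysis in SAP 4.2.4.2.

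The first option needs a change to both protocol and SAP wording, plus one term in the code. The second needs SAP wording only, since Protocol 9.4.3.1 leaves the list of sensitivity analyses open. The variable is already collected and derived. With either option, say that the adjusted ratio assumes a common effect across eosinophil groups and would weight the groups differently if that fails.
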